## 7.6. Blinded Photography Evaluation

Blinded photography evaluation will be performed by three physicians (plastic surgeons) to determine if the force modulating tissue bridges (FMTBs) are effective in improving the appearance of postoperative scars.

Three qualified, non-treating clinicians will be trained to independently review standard photographs for each subject taken at 12 months postoperatively. The reviewers will be blinded to subject information and to information regarding the closure technique utilized. No information will be provided to the reviewers that may allow them to determine which closure technique, FMTBs or suture, was used.

A pair of photographs (labeled A and B) for each subject will include the FMTB closure and the suture closure at 12 months postoperatively. The blinded reviewers will be asked to review a presentation of each subject's photographs and rate which scar has healed better of the options on the screen (A & B).

Additionally, each scar image will be organized individually, and the blinded reviewers will score each photograph using the Manchester Scar Scale (MSS).

		POI	NTS score)
SCAR CATEO	SORY	Untreated Area	Treated
Colour	Perfect	1	
	Slight mismatch	2	
	Obvious mismatch	3	
	Gross mismatch	4	
Shine	Matte	1	
	Shiny	2	
Contour	Flush with surrounding skin	1	
	Slightly proud/indented	2	
	Hypertrophic	3	
	Keloid	4	
Distortion	None	1	
	Mild	2	
	Moderate	3	
	Severe	4	

The identified reviewers will be instructed that their participation is completely voluntary and has no impact on performance review at their institution. It will be clearly stated that consent is implied with the institution's survey completion. No identifying information about these blinded reviewers will be published but will be maintained in a secure manner by the research team. A wavier of documentation is requested

as no subject Personal Health Information (PHI) will be collected, recorded or shared. Prior to completing the review, the study PI/coordinator will ask for a verbal consent from the reviewers indicating approval to use their responses in the study.

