## 2.2. Sample Size/Power Analysis Factors:

The sample size calculation will be determined by the primary outcome: POSAS-O score. The study will enroll 42 patients which will allow us to detect a moderate effect (Cohen's d=0.5) in scar quality measured by POSAS-O with at least 80% power, accounting for an estimated 20% loss of patients.

In a study evaluating the effect of platelet-rich plasma glue on surgical scars following breast reduction mammoplasty, the control group had a mean POSAS-O score of 20.4 (SD 12.5) at 1-year. Although a minimal

clinically important difference (MCID) for POSAS has not been established in the literature, Cohen's d effect size (0.2 represents "small" effect, 0.5 represents "moderate" effect, 0.8 represents "large" effect) can be used to estimate a difference that may be clinically important.

	Effect Size (Cohen's d)			
	0.2	0.3	0.4	0.5
Change in POSAS-O score	2.5	3.75	5	6.25
Proportional change to	4.2%	6.3%	8.3%	10.4%
maximum POSAS-O score				

	Effect Size (Cohen's d)			
Power	0.2	0.3	0.4	0.5
80%	199	90	52	34
85%	227	102	59	38
90%	265	119	68	44

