## 3.2. Primary Outcomes

- Patient and Observer Scar Assessment Scale (POSAS)
- Photographic Assessment

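### The side-by-side photo item records only which scar looked better; a graded preference from the same three reviewers would recover about 8 to 10 points of power at little cost

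*Combined protocol and SAP*

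**What the plan says.** Section 3.2 lists two primary outcomes, POSAS and "Photographic Assessment". The second is not defined further there.

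Section 7.6 describes the photographic review. "Three qualified, non-treating clinicians will be trained to independently review standard photographs for each subject taken at 12 months postoperatively". Each patient's FMTB side and suture side are shown as a pair labelled A and B, and the reviewers are to "rate which scar has healed better of the options on the screen (A & B". The options named are A and B. No strength of preference, no tie answer, no rule for combining three reviewers and no test is given.

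The same section then adds a second task: "Additionally, each scar image will be organized individually, and the blinded reviewers will score each photograph using the Manchester Scar Scale (MSS". The printed scale has four items: colour 1 to 4, shine 1 to 2, contour 1 to 4, distortion 1 to 4. The total therefore runs from 4 to 14.

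Section 2.2 sizes the trial on the other primary outcome: "The sample size calculation will be determined by the primary outcome: POSAS-O score". The 42 patients are meant to "allow us to detect a moderate effect (Cohen's d=0.5) in scar quality measured by POSAS-O with at least 80% power". No power is stated for any photographic measure.

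**The concern.** The trial is paired so that each patient is her own control (section 2.1). The information lies in how far the two scars of one patient differ. A two-option question cuts that difference at zero: a barely visible advantage counts the same as an obvious one, and a pair the reviewer cannot tell apart, if it is answered at all, becomes a vote for one side at random.

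The photographic review is also the only assessment for which section 7 describes blinded raters. Section 7.5 has the observer part of POSAS completed by a clinician at the visit and mentions no blinding. If the A/B answer is taken as the photographic result, the comparison best protected against rater expectation would rest on the coarser of the two ratings collected. It could miss an effect that a graded rating of the same photographs by the same people would show.

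**Working it through.** **Inputs.** From section 2.2: d = 0.5, at least 80% power, 34 patients in the table, 42 enrolled, 20% loss. From section 7.6: three independent reviewers. Assumed, because the plan is silent: two-sided 5%; normally distributed differences; d = 0.5 carried from POSAS-O to the photo rating, with 0.4 to 0.7 shown; and the agreement between reviewers.

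**Step 1: reproduce the plan's figure.** Paired t-test power is P(|T| > t(0.975, n−1)), where T is noncentral t with n−1 degrees of freedom and noncentrality d√n. For n = 34 and d = 0.5 the noncentrality is 0.5 × 5.83 = 2.92 and power is 80.8%. The same formula returns all twelve cells of the plan's table (for d = 0.5: 34, 38 and 44), which supports the two-sided 5% assumption. Enrolment: 34 / 0.8 = 42.5, and 42 × 0.8 = 33.6, so 42 is within one patient.

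**Step 2: one binary result per patient.** P(FMTB preferred) = Φ(d) = Φ(0.5) = 0.691. With 34 patients the exact two-sided sign test needs 24 or more for one side; its actual size is 0.024.

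| n | d | Paired t | Exact sign test | Loss (points) |
|---|---|---|---|---|
| 34 | 0.4 | 62.0% | 33.6% | 28 |
| 34 | 0.5 | 80.8% | 51.1% | 30 |
| 34 | 0.6 | 92.4% | 68.2% | 24 |
| 34 | 0.7 | 97.7% | 82.0% | 16 |
| 33 | 0.5 | 79.5% | 55.7% | 24 |
| 42 | 0.5 | 88.6% | 70.2% | 18 |

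Part of the loss at n = 34 is discreteness of the exact test. The normal-approximation sign test gives 61.6%, a loss of 80.8 − 61.6 = 19 points.

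**Step 3: three reviewers, n = 34.** Simulation, 6,000 runs. Reviewer j's perceived difference for patient i is μ + b(i) + e(ij), with var(b) = ρ and var(e) = 1 − ρ. μ is set so that the three-reviewer mean has the stated d. The no-difference zone takes about a quarter of ratings. Counted votes means the number of reviewers choosing FMTB (0 to 3), compared with 1.5 by a t-test. Results at d = 0.5:

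| ρ | Majority vote, exact sign test | Counted votes | Five-point, summed | Continuous rating |
|---|---|---|---|---|
| 0.3 | 46.3% | 69.0% | 78.6% | 80.7% |
| 0.5 | 48.5% | 70.6% | 79.2% | 81.1% |
| 0.7 | 48.8% | 70.0% | 78.5% | 80.2% |
| 0.9 | 50.9% | 69.8% | 78.9% | 80.9% |

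- Five-point minus counted votes: 9.6, 8.6, 8.5 and 9.1 points. This is the cost of the response format. A second simulation (20,000 runs, ρ from 0.4 to 0.8) gave 8.2 to 9.8.
- Five-point minus majority vote: 32.3, 30.7, 29.7 and 28.0 points. This adds the cost of collapsing the votes and of the conservative test.

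**Step 4: sensitivity of the format cost to d (n = 34, same four values of ρ).**

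| d | Counted votes | Five-point | Difference (points) |
|---|---|---|---|
| 0.4 | 49.7 to 52.7% | 59.7 to 61.1% | 7.5 to 10.7 |
| 0.6 | 82.9 to 85.7% | 90.9 to 91.5% | 5.7 to 8.0 |
| 0.7 | 92.3 to 93.9% | 96.6 to 97.2% | 3.2 to 4.6 |

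With all 42 patients evaluable, d = 0.5 and ρ = 0.5, counted votes give 79.7% and five-point 87.6%, a difference of 7.9 points.

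**The case against.** The strongest reply is that graded blinded data are already planned. The Manchester score records both degree and equality, comes from the same reviewers on the same photographs, and its paired difference costs nothing to compute. Section 7.7 adds quantitative image measures. A reader might infer that the photographic primary outcome as a whole has been reduced to a binary vote. The documents do not support that: section 3.2 does not define the outcome as the A/B answer, and the word introducing the Manchester scoring does not rank one measure above the other. What remains is that nothing makes the Manchester score the photographic result either.

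A reader might also infer that the two-option format by itself costs about 30 points. It does not. That figure needs a majority vote or a single rating per patient, plus an exact sign test whose actual size at n = 34 is half the nominal level. The plan specifies none of these.

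Third, d = 0.5 is stated for POSAS-O only, and no power is claimed for photographs. It would therefore be wrong to say that the item falls short of a target the plan set for it. The figures compare formats under a common assumed effect; at larger effects the gap narrows but keeps its direction.

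Finally, section 7.6 describes the question, not the rating form. It does not say that a tie is barred, only that none is named. All of these points stand, and they limit the size of the finding rather than remove it.

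**Conclusion.** The point holds in a limited form. As written, the side-by-side item records only the direction of the within-patient difference. Under the stated assumptions (d = 0.5 borrowed from POSAS-O, normal differences, two-sided 5%, 34 evaluable patients, the same underlying effect for every format), this costs about 8 to 10 points of power against a five-point preference when the votes are counted, and about 4 points at d = 0.7. Because the analysis is unspecified, the realised loss could be larger, up to about 30 points under the least efficient handling of the votes. That upper figure describes an analysis the plan leaves open, not one it adopts. Since graded Manchester scores will exist, this is a cheap improvement and not a flaw that threatens the trial.

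**What to change.** Either of two changes to section 7.6, made before the 12-month photographs are rated, or at least before the A/B labels are decoded:

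1. Replace the two-option choice with five answers: A much better, A slightly better, no difference, B slightly better, B much better. Decode to FMTB versus suture after rating, average over the three reviewers, and analyse one signed score per patient with a paired t-test or a Wilcoxon signed-rank test. If the latter is chosen, say how zeros are handled.
2. Keep the A/B question as descriptive, and state that the photographic result is the within-patient FMTB-minus-suture difference in Manchester total, averaged over the three reviewers. The documents give no standard deviation for this score, so its power cannot be worked out from them.

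The first costs one altered question and one analysis sentence; the second needs no new data. Neither adds patients, visits or readers. The downside of the first is a slightly finer judgement for the reviewers, and the percentage preferring FMTB becomes a summary derived from the graded answers.

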## 7.7 ImageJ Scar Area Analysis

Photographs will be analyzed using ImageJ software to quantitatively measure pigment, redness, surface area, and volume of the scar area. Chroma and pigmentation from the images will be obtained using the Pantone Connect extraction. The scar area where noninvasive measurements were obtained with the skin around it will be analyzed.

## 8. POTENTIAL RISKS

## Allergic Reaction: (Rare <5%)

There is a possibility of an allergic reaction to the adhesive on the device. Subjects will be questioned with regard to any history of allergies and carefully monitored for signs of allergic reaction during pre-screening.

## Wound Infection: (Rare)

While subjects may experience many side effects after their surgery including but not limited to: oozing, strong pain, swelling persisting for more than 24 hours, or signs of infection (e.g., pus, drainage, fever) are cause for immediate concern and they should contact the investigator and/or his designee, to be evaluated. In the first 216 breasts treated with FMTBs, there have been no reports of wound infection.

## Irritation & Blistering: (Rare <5%)

A crust, blister or superficial wound can occur at the treatment area. The risk of infection will be minimized by proper wound care. Subjects will be requested to contact a member of the research team should irritation or blistering occur at any time point after surgery.

## Hypertrophic or Keloidal Scar: (Rare)

There is a small risk for abnormal scarring with any wound closure technology. However, this is minimized by proper technique and wound care. This risk may be higher if the patient has a prior personal or family history of pathologic scarring. In the first 216 breasts treated with FMTBs, there have been no reports of hypertrophic or keloidal scar.

Symptoms including the examples discussed above, will not be treated as adverse reactions if they are mild in nature. These conditions may or may not resolve over time. Symptoms that are persistent and moderate to severe in nature, or that involve elevation (e.g. edema, papules, vesicles, spreading) will be considered AEs. The Investigator will have the final determination as to whether a reaction will be considered an AE.

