## 6.4.1 Post-Surgical Procedures

- Subjects will be provided standardized instructions to encourage wound care for a total of 8 weeks.
- Supporting products (dressings etc.) will be provided to ensure compliance and an adequate supply to change dressing before next visits.
- 6.5. Wound Therapy Visits: Visits 3-6 (Weeks 2,4,6 and 8)
  - 1. A clinician will record any changes to the subjects' concomitant medications and will ask subjects if they have experienced any changes in their health since the previous visit. If an adverse event (AE) is reported, then the Investigator will be informed and an AE form will be completed.
  - 2. A clinician will clean and assess wounds. FMTB will be reapplied every two-weeks. If the visit

is being performed virtually, via telehealth, than the patient will be observed while cleaning his/her wound as well as during the reapplication of the FMTBs.

- 3. If in person, photographs will be taken of the wounds as described in section 7.1
- 4. If in person, skin lab measurements will be taken at visits 4 and 6 (weeks 4 and 8) as described in section 7.2.
- 5. If in person, biopsy samples will be obtained at visits 4 and 6 (weeks 4 and 8) as described in section 7.3
- 6. Supporting products will be provided to subject to ensure compliance. If patients opt to have telehealth visits for visits 4 and 6, FMTBs will be provided, as well as alcohol swabs for cleaning the skin. Patients will also be properly trained on how to apply the FMTBs themselves at prior visits if they plan to opt for telehealth visits.

These visits will take about 45 minutes

- 6.6. Follow-Up Visits: Visit 7-9 (Months 3, 6 and 12)
  - 1. A clinician will record concomitant medications and will ask subjects if they have experienced any changes in their health since the previous visit. If an adverse event (AE) is reported, then the Investigator will be informed and an AE form will be completed.
  - 2. Photographs will be taken of the wounds as described in section 7.1
  - 3. Skin lab measurements will be taken during each visit as described in section 7.2
  - 4. Biopsy samples will be obtained as described in section 7.3
  - 5. Patient and Observer Scar Assessment Scale will be completed by both the subject and clinician as described in section 7.4.

These visits will take about 45 minutes

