## 7. ASSESSMENTS

## 7.1. Photography Procedures

Prior to photography procedures, clinic personnel will ensure that subjects will remove any jewelry and clothing from the area(s) to be photographed and equilibrate for at least 15 minutes to ambient conditions within the clinic before any photographs are taken.

1. Nikon D7200

Standard and close-up photography will be utilized for evaluation of the appearance surgical scars. These photographs will be taken utilizing the Nikon D7200 at screening/baseline, week 2, week 4 (if in-person), week 6 (if in-person), week 8, 3-month post-surgery, 6-months post-surgery and 12-months post-surgery.

2. e-Kare

e-Kare 3D wound management software will be used to obtain high quality 3D wound images in real time that will provide wound dimensions, max depth, surface area and volume.

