## 8.1. Adverse Events

At each visit, the Investigator will question the subject about adverse events using an open-ended question. If a potential adverse event is reported by the subject or identified during examination, directed questioning and examination will be performed when appropriate. At this time, the following will be performed:

1. Obtain a complete history of the event in question as well as conduct an examination of the subject and determine if the reported event qualifies as an Adverse Event. If the event is

determined to be an Adverse Event, an Adverse Event (AE) case report form and Event Follow-up (EF) Visit case report form must be completed. One AE case report form should be used to track the history of an individual AE throughout the period of the study.

- 2. Collect an updated medical and surgical history along with recording of concomitant medications or treatments.
- 3. Take photographs of the subject with attention to the area in question.
- 4. Render treatment for the event, if any, as determined by the medical judgment of the investigator.

Photographs will be taken to document any AEs if possible.

For the duration of the study, medical assistance will be provided to the subject for study-related problems at no expense, if in the opinion of the Investigator, the reaction was caused by the study device. Should a subject choose to seek their own medical treatment, no reimbursement will be offered.

When an AE persists at the end of the study, the Investigator will ensure a follow-up of the subject until the Investigator believes that the event is satisfactorily resolved.

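### Mild, non-elevated skin and wound events in weeks 0 to 8 have no specified event record, and no by-breast count of acute events is planned, although section 2 sets out to quantify tolerability and T-junction benefit

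*Combined protocol and SAP*

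**What the plan says.** Section 8 lists allergic reaction, infection, irritation and blistering, and hypertrophic or keloidal scar as risks. The irritation entry reads: "A crust, blister or superficial wound can occur at the treatment area". The rule after the last entry is: "Symptoms including the examples discussed above, will not be treated as adverse reactions if they are mild in nature". The next sentence makes two kinds of symptom AEs: those that are both persistent and moderate to severe, and those "that involve elevation (e.g. edema, papules, vesicles, spreading) will be considered AEs". The paragraph ends: "The Investigator will have the final determination as to whether a reaction will be considered an AE".

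Section 8.1 starts with a work-up: "If a potential adverse event is reported by the subject or identified during examination, directed questioning and examination will be performed when appropriate". Form completion then depends on the Investigator's judgement: "determined to be an Adverse Event, an Adverse Event (AE) case report form and Event Follow-up (EF) Visit case report form must be completed".

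Section 2 (Background) reports survey feedback that the devices improve early scars and are well tolerated, and an anecdotal link with fewer T-junction wound complications. It then says the study is meant to confirm and quantify these benefits. Section 3.1 names photography, skin assessments and POSAS as the means of analysing effects. The outcome lists in 3.2 and 3.3 contain no wound-complication or skin-reaction outcome.

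**The concern.** The device is held on the skin by adhesive for 8 weeks, so irritation, blistering and minor wound problems are the short-term events that section 8 itself expects. The recording rule drops the mild ones before any form is completed. A sparse list of skin-reaction AEs could then reflect the rule as much as good tolerability.

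The within-patient design, with one breast per closure method, suits a side-by-side description of these events, but none is planned. The tolerability and T-junction statements in section 2 would have no planned table behind them. Events not logged when they happen can be recovered later only in part.

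**Working it through.** **The recording rule, case by case**

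| Event in weeks 0 to 8 | Section 8 wording | AE form under 8.1 |
|---|---|---|
| Mild, non-elevated | Excluded as mild | Not required |
| Any severity, with elevation | AE, reading the elevation clause as an exception to the mild rule | Required |
| Persistent, moderate to severe | AE | Required |
| Moderate to severe, transient, non-elevated | Fits neither sentence | Investigator decides |

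The first row has no specified event record. The last row has no rule.

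**What else is collected**

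- Section 6.5: a clinician cleans and assesses the wounds and asks about health changes. No graded or by-breast tally is specified.
- Photographs in section 6.5: "If in person, photographs will be taken of the wounds as described in section 7.1". Section 7.1 agrees: "week 4 (if in-person), week 6 (if in-person").
- Section 8: subjects are asked to contact the team about irritation or blistering, with no severity threshold stated.
- Section 8.1: a potential AE gets a history, an examination and photographs.
- Sections 7.2 and 7.4: TEWL and colorimetry are measurements, not event counts.
- Section 7.5 and the schedule in 6.1: POSAS pain and itch are collected from week 8, the end of device wear.
- Section 7.6: blinded clinicians score each scar photograph at 12 months on the Manchester scale, whose contour item has hypertrophic and keloid grades. This covers pathological scars, so they lie outside this point.

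None of these is specified as a count of acute events by side. Together they would support a partial, unplanned reconstruction.

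**Size, for illustration only**

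The plan gives no figure for AE counts. Its only sizing is for POSAS-O: 34 pairs for d = 0.5 at 80% power. A paired t-test at two-sided 0.05 (alpha is assumed, as none is stated) reproduces 34, with power 80.8%. Nothing here changes that.

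Inputs:

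- n = 42 device breasts (sections 2.2 and 3.1).
- Reaction rate p per device breast. Section 8 gives under 5% for allergic reaction and, separately, under 5% for irritation and blistering, neither stated per breast. I assume a combined p of 5% to 10%.
- Share m of reactions that are mild and non-elevated. This is not in the documents; I assume 0%, 25%, 50% and 80%.
- Patients are independent.

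Expected recorded events = n × p × (1 − m). Chance of none = (1 − p(1 − m))^n.

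| m | Expected, p = 5% | Chance of none, p = 5% | Expected, p = 10% | Chance of none, p = 10% |
|---|---|---|---|---|
| 0% | 2.10 | 0.95^42 = 12% | 4.20 | 0.90^42 = 1% |
| 25% | 1.58 | 0.9625^42 = 20% | 3.15 | 0.925^42 = 4% |
| 50% | 1.05 | 0.975^42 = 35% | 2.10 | 0.95^42 = 12% |
| 80% | 0.42 | 0.99^42 = 66% | 0.84 | 0.98^42 = 43% |

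These are chances of no recorded device-side skin-reaction AE.

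**What full logging could show**

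With zero events, the two-sided 95% exact upper limit is 1 − 0.025^(1/n): 8.4% for n = 42 and 10.3% for n = 34. Exact McNemar power with 34 to 42 pairs, at assumed discordant rates of 10% (device only) and 1% (suture only), is 9% to 18%. At 20% and 2% it is 50% to 65%. A comparison by side would therefore be descriptive unless reactions are common.

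**The case against.** The strongest reply is that the plan already watches these patients closely, through the visits, photographs and patient contact listed above. The Investigator also monitors subject experience (section 9.2) and can class any reaction as an AE. The device is Class 1 and non-significant risk, the aim in section 2 is background prose, and the operative outcomes in section 3 make no tolerability or T-junction claim. Much of this stands. It shows that the gap lies in recording and reporting rather than in attention to patients, and that section 2 needs only a wording change. It does not supply an event count by side, and the Investigator's final say makes recording more discretionary.

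A reader might also infer more than the text supports:

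- *No complication is assessed by side.* Not so: the Manchester scoring covers hypertrophic and keloid scars.
- *The blister example and the vesicle clause flatly contradict each other.* The conflict largely disappears if elevation is an exception to the mild rule, which is the natural reading. Likewise, the shift from adverse reactions to AEs is weak evidence of inconsistency, because the paragraph's last sentence links the two.
- *5% is the protocol's ceiling for all reactions.* Section 8 gives two separate risks, so the combined rate could approach 10% if they do not overlap.
- *The table gives the chance of an empty AE listing.* It covers skin reactions only; the listing would also hold infection, dehiscence and other events.
- *The forms do not capture side.* The case report forms are not shown, so this is unknown.

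**Conclusion.** The point holds for acute wound events and device-wear skin reactions. As written, mild, non-elevated events have no specified record, transient moderate-to-severe non-elevated events have no rule, and no by-breast count is planned to support two of the benefits named in section 2.

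The reading that the rule biases the trial in favour of the device is not supported. It applies to both breasts, and neither the size nor the direction of any bias can be computed from the documents. Persistent moderate-to-severe reactions and elevated reactions are still captured as AEs.

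The illustrated effect depends on the assumed rate and mild share: across 5% to 10%, a mild share of one half moves the chance of no recorded skin-reaction AE from 12% to 35%, or from 1% to 12%. This is a cheap improvement rather than a flaw in the main analysis.

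**What to change.** Recording and reporting only; patient care stays as it is.

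1. Reconcile the section 8 sentences so that the mild exclusion does not govern what is recorded. State whether elevation is an exception to it, and how a transient, moderate-to-severe, non-elevated reaction is classed.
2. At each visit, including telehealth, log every acute wound or skin event by breast, location (including the T-junction), severity, and start and end dates, whether or not it is classed as an AE.
3. Add these events to section 3.3 as a descriptive secondary outcome. Report them by side, for all grades and for moderate to severe, with the paired difference and a small-sample 95% interval (the Tango score interval is one option), and no confirmatory test.
4. In section 2, say that the study will *describe* tolerability and T-junction complications.

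The cost is more form entries, one table and a wording change. Reported event counts will look higher, and the intervals will be wide.
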